## 7.1 Demographics and Baseline Characteristics

Continuous demographic variables include age, weight, height, and body mass index (BMI). Categorical demographic variables include sex, ethnicity, race, age ( $\leq 35$ ,  $> 35$  years), BMI ( $< 25$ ,  $25 - < 30$ ,  $\geq 30$  kg/m^2), tobacco user (current, former, never, unknown), and alcohol user (current, former, never, unknown).

Continuous baseline characteristics include MBL volume, hemoglobin concentration, International Federation of Gynecology and Obstetrics (FIGO) classification, fibroid and uterine volume. Categorical baseline characteristics include Physician Surgery Questionnaire (PSQ), Reason for Study Participation Questionnaire, and hemoglobin concentration ( $\leq 10.5$ ,  $> 10.5 - \leq 12$ , and  $> 12$  g/dL).

### **Baseline Fibroid and Uterine Volume**

Fibroid and uterine volume data will be summarized at Baseline with data as observed; missing data will not be imputed.

For each subject, the fibroid with the largest volume at Baseline is considered as the primary fibroid for the subject. Baseline average fibroid volume is calculated using the average volume of fibroids with measurements available at Baseline.

### **FIGO Classification**

The number and percentage of subjects with fibroids at each location (e.g., intramural, subserosal, submucosal non-pedunculated, and subserosal pedunculated) according to the FIGO classification will be summarized for each treatment group at Baseline. For each subject, the lowest FIGO classification among all measurements of all fibroids before or on Day 1 (or before Day 8 if there is no measurement before or on Day 1) will be considered as the Baseline FIGO for the subject.

## **7.2 Medical History**

Medical history data will be coded using the Medical Dictionary for Regulatory Activities (MedDRA). The actual version of the MedDRA coding dictionary will be noted in the statistical tables and clinical study report. The number and percentage of subjects in each medical history category (by MedDRA system organ class and preferred term) will be summarized overall and by treatment group. The system organ class (SOC) will be presented in alphabetical order, and the preferred terms will be presented in alphabetical order within each SOC. Subjects reporting more than one condition/diagnosis will be counted only once in each row (SOC or preferred term). Non-gynecological medical history, gynecological medical history, menstrual and obstetrical history will be summarized and presented separately.

## **7.3 Prior and Concomitant Medications**

Prior and concomitant medications will be summarized by generic name. A prior medication is defined as any medication taken prior to the date of the first dose of study drug. A concomitant medication is defined as any medication that started prior to the date of the first dose of study drug and continued to be taken after the first dose of study drug or any medication that started on or after the date of the first dose of study drug, but not after the date of the last dose of study drug. A medication will be considered a concomitant medication where one of the following three cases occurs (1) the start date is missing and the end date is either after or on the first study drug dose date; (2) the start date is prior to or on the last dose of study drug and the end date is missing; (3) both the start date and the end date are missing.

The number and percentage of subjects taking medications will be summarized by generic drug name based on the World Health Organization (WHO) Drug Dictionary for both prior and concomitant medications.

## **8.0 Efficacy Analyses**

### **8.1 General Considerations**

All efficacy analyses will be conducted in the FAS Population. All tests will be 2-sided at an alpha level of 0.05.

Unless otherwise specified, categorical data will be summarized by frequency and percentage; descriptive summaries of continuous data will display the mean, SD, median, minimum, and maximum.

For continuous variables, when the analyses of change and/or percent change from Baseline to post-baseline visit(s) are performed, the within-group change from Baseline to each applicable visit will be summarized by treatment group with the mean, SD (or SE), and 95% Confidence Intervals (CIs). The between-group differences will be summarized with the mean, SE, 95% CIs, and P value when applicable. At each post-baseline visit, the Baseline mean and post-baseline visit mean will be calculated for all subjects with baseline and post-baseline value at that visit by treatment group.

Final Month is defined as the last 28 days prior to and including the last dose day.

Unless otherwise specified, there is no hypotheses testing for efficacy endpoints in the Post-Treatment Follow-up Period.

Information regarding corresponding statistical methods for analyses and any additional statistical measures required for a specific variable/endpoint will be provided in relevant sections.

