7.3 Statistical Analyses for Efficacy

Primary Efficacy Analysis

The primary efficacy analysis will be based on the FAS, and the primary endpoint will be the proportion of responders meeting the following conditions:

- MBL volume < 80 mL at the Final Month (the last 28 days of treatment)
- $\geq 50\%$ reduction in MBL volume from Baseline to Final Month (the last 28 days of treatment)

Subjects whose primary reason for prematurely discontinuing study drug is "lack of efficacy," or "requires surgery or invasive intervention for treatment of uterine fibroids" will be considered as non-responders.

The primary endpoint will be analyzed using a logistic regression model including treatment as the main effect and baseline MBL volume as a covariate. Missing Final Month MBL volume will be imputed using multiple imputation. For subjects who prematurely discontinue the Treatment Period prior to Month 6, the Final Month (the last 28 days prior to and including the last dose date) will be used in the primary analysis.

Additional Efficacy Analyses

Details on other efficacy analyses are provided in the SAP.

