### **3.0 Endpoints**

#### **3.1 Primary Endpoint(s)**

The primary endpoint will be the proportion of subjects meeting both of the following conditions:

- Menstrual blood loss (MBL) volume < 80 mL at the Final Month (the last 28 days of treatment), and
- $\geq 50\%$  reduction in MBL volume from Baseline to the Final Month (the last 28 days of treatment).

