#### **8.3.3 Primary Efficacy Analysis**

The primary analysis of the primary endpoint will be performed using the full analysis set population.

If a subject has missing observed Final Month MBL volume, the Final Month MBL volume will be imputed using multiple imputation as described in Section 8.2.

The primary analysis of the primary efficacy endpoint with multiple imputation will be carried out in the following steps:

1. **Multiple Imputation:** 30 "complete" datasets of monthly MBL volume from Month 1 to Month 6 will be generated using SAS PROC MI as described above. The following covariates will be used in the imputation model:
  - a. Baseline MBL volume

- b. Randomized treatment group
  - c. Baseline hemoglobin
  - d. MBL volume in prior months
  - e. Age of the subject at Baseline
2. **Impute Final Month MBL Volume:** In each of the 30 generated datasets, subject's missing Final Month MBL volume will be imputed using the MBL volume from the "complete" dataset with Month 1 – 6 MBL volume by looking at the corresponding month of the last dose day using analysis time window. Subjects whose last dose day are the same as Study Day 1 will have their Final Month MBL volume imputed using their Month 1 MBL volume.
3. **Impute Responder Status:** The responder status (yes/no) will be derived from "complete" (observed or imputed) Final Month MBL volume, using the criteria as described in Section 8.3.1. Subjects whose primary reason for prematurely discontinuing study drug is "lack of efficacy," or "requires surgery or invasive intervention for treatment of uterine fibroids" will be considered as non-responders.
4. **Analysis:** Each of the 30 imputed datasets will be analyzed separately using a logistic regression model including treatment as the main effect and Baseline MBL volume as a covariate to compare the elagolix treatment group to placebo.
5. **Pooling:** Estimates of the proportions of responders in each treatment group and the difference between the proportions from the 30 imputed datasets obtained from step 3 will be combined into one overall result using PROC MIANALYZE in SAS.

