### **Amenorrhea**

The number and percentage of subjects who achieve amenorrhea will be calculated for each treatment group. The amenorrhea analysis includes subjects on study drug for at least 38 days. For each subject, amenorrhea at the Final Month is defined as having 0 days of bleeding or spotting during the last 28 days prior to and including the last dose day, with the interval starting at or beyond Study Day 11. If a subject does not have evaluable AH data during the last 28 days and no bleeding or spotting or "There was no visible blood on the sanitary products" is indicated on UBQ, then she is considered amenorrheic. The denominator will be the number of subjects with at least 38 days on study drug and having an amenorrhea status at the Final Month. The number and percentage of subjects with amenorrhea at Final Month will be summarized by treatment group and compared between the elagolix treatment group and placebo using the Miettinen-Nurminen (M-N) method.

Time to amenorrhea is defined as the number of days from the first study drug dose date to the day a subject achieves amenorrhea (i.e., the day a subject achieves amenorrhea – the first study drug dose date + 1). For a subject who achieves amenorrhea, the day she achieves amenorrhea is defined as the next day of the last bleeding/spotting day during the Treatment Period. The median, Q1, and Q3 of time to amenorrhea will be calculated for subjects who achieve amenorrhea using Kaplan-Meier method.

In the monthly analysis of bleeding for amenorrhea, the numerator will be the number of subjects on treatment who do not bleed or have spotting during the specified time window specified in [Table 1](#) (but may have begun bleeding or spotting thereafter) and the denominator will be the number of subjects on study drug for the full window and having an amenorrhea status for that month.

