### **Suppression of bleeding**

Suppression of bleeding is defined similarly to amenorrhea except that spotting is allowed. For each subject, achieving suppression of bleeding at the Final Month is defined as having 0 days of bleeding (spotting allowed) during the last 28 days prior to and including the last dose day with the interval starting at or beyond Study Day 11. The

suppression of bleeding analysis includes subjects with at least 38 days on study drug. If a subject does not have evaluable AH data during the last 28 days and no bleeding is indicated on UBQ ("Subject only had spotting that did not require the use of sanitary products" or "There was no visible blood on the sanitary products" is allowed), then the subject will be considered having achieved suppression of bleeding. The denominator will be the number of subjects with at least 38 days on study drug and having a suppression of bleeding status at the Final Month.

The number and percentage of subjects achieving suppression of bleeding at Final Month will be summarized by treatment group and compared between the elagolix treatment group and placebo using the Miettinen-Nurminen (M-N) method.

Time to suppression of bleeding is defined as the number of days from the first study drug dose date to the day a subject achieves suppression of bleeding (i.e., the day a subject achieves suppression of bleeding – the first study drug dose date + 1). For a subject who achieves suppression of bleeding, the day she achieves suppression of bleeding is defined as the next day of the last bleeding day during the Treatment Period. The median, Q1, and Q3 of time to suppression of bleeding will be calculated for subjects who achieve suppression of bleeding using Kaplan-Meier method.

Monthly analysis of bleeding for suppression of bleeding, incidence and cumulative incidence of suppression of bleeding will be provided in the same way as will be done for amenorrhea in [Table 1](#) and [Table 2](#). Plots will be provided by treatment group for percentage of subjects with incidence and cumulative incidence of suppression of bleeding during the Treatment Period, respectively.

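### Does the primary endpoint's Final Month need a minimum time on study drug, like the 38-day rule for amenorrhea and suppression of bleeding?

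*SAP*

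**What the plan says.** SAP 8.1 gives the general definition: "Final Month is defined as the last 28 days prior to and including the last dose day". Protocol 7.3 applies the same look-back to women who stop before Month 6: "the Final Month (the last 28 days prior to and including the last dose date) will be used in the primary analysis". The endpoint statement in SAP 3.1, like Protocol 3.2, is worded differently: "volume < 80 mL at the Final Month (the last 28 days of treatment", that is, 28 days on treatment.

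The full analysis set requires one dose only. The one short-exposure rule for the primary endpoint is in SAP 8.3.3, step 2: "Subjects whose last dose day are the same as Study Day 1 will have their Final Month MBL volume imputed" from Month 1. Other missing Final Month volumes are filled by "looking at the corresponding month of the last dose day using analysis time window".

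Two secondary bleeding measures in SAP 8.4 are stricter. For amenorrhea: "The amenorrhea analysis includes subjects on study drug for at least 38 days", "with the interval starting at or beyond Study Day 11". For suppression, the "suppression of bleeding analysis includes subjects with at least 38 days on study drug", with the same Day 11 start. Change in MBL volume at the Final Month has no such rule; it uses the volumes from the primary analysis.

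**The concern.** For a last dose on Days 2-27 the two wordings cannot both hold, because there are not 28 treated days. Dosing starts on Days 1-10 of a menses (Operations Manual 2.2, Day 1 notes), and products are collected continuously from Screening (Operations Manual 3.22). A look-back window can therefore include pre-dose menses, while a window cut at Day 1 or Day 2 can fall almost entirely in the bleed-free part of the cycle.

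The same collected data can then give opposite results. Take a 28-day cycle, a 5-day front-loaded menses, a 150 mL baseline, dosing from cycle day 5 and a stop for an adverse event on Day 14. The on-treatment window holds about 13 mL (responder). The look-back holds the full 150 mL (non-responder).

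For a last dose on Days 28-37 the window is defined, but in a long cycle it can miss most of a menses. The non-responder and observed-case sensitivity analyses act only on a missing Final Month, so they do not vary the window. With 16 placebo women and 16 x 0.10 = 1.6 expected responders, one reclassified woman moves that arm by 1/16 = 6.25 points. Since the SAP protects two other endpoints from short exposure, the primary endpoint looked overlooked.

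**Working it through.** **The plan's own figure.** Inputs from SAP 2.4: 32 v 16 women, 55% v 10% responders, two-sided alpha 0.05. Exact enumeration with Fisher's test gives power 0.865, consistent with the stated 80% or more.

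**The 38-day and Day 11 rules are one rule.** A 28-day window ending on Day 38 starts on 38 - 28 + 1 = Day 11.

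**Illustrative model, no drug effect (assumptions, not trial data).** Dosing starts on cycle day 1-10, equally likely. Menses last 5 or 7 days with front-loaded flow (20/30/22/13/8, then 5/2 for the 7-day case, rescaled). Cycles are 24, 28, 32 or 38 days, equally weighted (criterion 18 allows 24-38). Baseline is 100, 150 or 250 mL. A woman responds if the window holds at most half of one menses and less than 80 mL.

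| Last dose | Cut at Day 2 | Cut at Day 1 | 28-day look-back |
|---|---|---|---|
| Days 2-27 | 0.781 | 0.679 | 0.044 |
| Days 28-37 | 0.224 | 0.218 | 0.218 |
| Days 2-37 | 0.626 | 0.551 | 0.092 |
| Days 38-168 | 0.086 | 0.086 | 0.086 |

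The look-back column is low for a simple reason: 28 consecutive days contain at least one full cycle's loss whenever the cycle is 28 days or shorter. By cycle length (24/28/32/38 days) the look-back gives 0/0/0.076/0.100 for Days 2-27 and 0/0/0.170/0.703 for Days 28-37. The 22% for Days 28-37 thus comes only from long cycles. The same feature persists after Day 38 (0.112 and 0.232), so a 38-day threshold would reduce it but not remove it.

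About half of the high on-treatment shares (0.414 of 0.781; 0.326 of 0.679) are women with no loss at all in the window.

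**What a 38-day rule would do.** If the Final Month were set to missing below 38 days, step 2 of SAP 8.3.3 would use imputed Month 1 for last doses up to Day 28 and imputed Month 2 for Days 29-37. In the same model a full Month 1 (Days 2-28) gives 0.342 responders and Month 2 gives 0.092. Over the 36 last-dose days from Day 2 to Day 37: (27 x 0.342 + 9 x 0.092) / 36 = 0.28, against 0.092 with the look-back.

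**Number of women.** The documents give no early-stopping rate. Assume a share d stops evenly over 168 days. By Day 27: 48 x d x 27/168 = 0.39 (d = 5%) to 1.54 (d = 20%). By Day 37: 48 x d x 37/168 = 0.53 to 2.11. On placebo by Day 27: 16 x d x 27/168 = 0.13 to 0.51. Multiplied by the gap between readings (0.679 - 0.044 = 0.635 to 0.781 - 0.044 = 0.737), that is 0.08 to 0.38 reclassified placebo women. Stops for lack of efficacy or fibroid surgery are non-responders by rule and would lower these counts.

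**Effect on the comparison.** Let e = d x 37/168 be the early share in each arm (1.1% or 4.4%) and q the responder share among early stoppers. Each arm's rate is (1 - e) x planned rate + e x q. With the same e and q in both arms, q cancels from the difference, which is (1 - e) x 0.45.

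| | Difference | Fisher power, cut at Day 2 | Fisher power, look-back |
|---|---|---|---|
| e = 1.1% | 0.445 | 0.852 | 0.857 |
| e = 4.4% | 0.430 | 0.813 | 0.831 |

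The reading is worth 0.5 to 1.8 points of power and leaves the expected difference unchanged. If early stoppers were instead imputed under missing at random at the planning rates (55% v 10%), the difference at e = 4.4% would return to 0.450 and power to 0.865.

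**The case for a change.** The strongest argument for a change is that the rule belongs to the primary endpoint, the trial has one database lock and one analysis, and a programmer who follows SAP 3.1 rather than SAP 8.1 could cut the window at treatment start. In a 16-woman placebo arm a single such case would be visible, and no planned sensitivity analysis varies the window. The two wordings do differ for last doses before Day 28, and neither document says so. That much stands.

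The step from there to a minimum-exposure rule does not. SAP 8.1 is the definition, Protocol 7.3 repeats it specifically for early stoppers, and the phrase in the endpoint statements reads as shorthand for it.

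The 38-day rule was written for endpoints that require no bleeding days (spotting allowed for suppression). There, leftover baseline menses alone would defeat the endpoint, and short-exposure women leave the denominator. In a volume endpoint analysed on the full analysis set, leftover menses pushes towards non-response and nobody is dropped. Different rules are defensible, and change in MBL at the Final Month also does without the 38-day rule.

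The Day 1 sentence in SAP 8.3.3 does not show that Days 2-27 were forgotten. Month 1 in the imputation runs from Day 2, so a last dose on Day 1 maps to no month and needs its own line; a last dose on Days 2-27 maps to Month 1 if the volume is missing.

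**Conclusion.** The gap is a missing detail that the plan's own definition fills sensibly. Followed as written, the 28-day look-back makes a very early stopper with no drug effect a responder about 4% of the time, below the 9% seen for last doses from Day 38. A 38-day set-to-missing rule would replace observed windows with imputed ones, raise the chance-responder share for last doses on Days 2-37 from 9% to about 28%, and at the planning rates move the expected difference from 0.430 to 0.450 in favour of elagolix (4.4% stopping by Day 37). It would help for Days 28-37 taken alone, but not overall.

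The stake is small: 0.4-1.5 of 48 women by Day 27, about 0.5-2 points of power, and no expected bias if early stopping is equal in the arms. Power stays above 80% under either reading. The amendment also describes the study as exploratory. These figures rest on the assumed 5-20% stopping spread evenly over 168 days and on the stylised cycle model. Early stopping that was much more frequent, or clearly unequal between arms, would make the reading matter more, but nothing in the documents points to that. No change to the plan follows.

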### **8.2 Handling of Missing Data**

Multiple Imputation (MI) will be used in the primary analysis for the primary endpoint.

Missing Final Month MBL volume will be imputed using multiple imputation. First, *M* "semi complete" datasets of monthly MBL volume (Month 1 [Day 2 – Day 28], Month 2

[Day 29 – Day 56], Month 3 [Day 57 – Day 84], Month 4 [Day 85 – Day 112], Month 5 [Day 113 – Day 140], and Month 6 [Day 141 – Day 168]) with monotone missing data pattern will be generated via MCMC option using SAS PROC MI. Then, for each of the  $M$  "semi complete" datasets with monotone missing data, a "complete" dataset of monthly MBL volume from Month 1 to Month 6 will be generated via MONOTONE REG option using SAS PROC MI.  $M$  represents the number of imputations and we set  $M = 30$ . The random seed 12345 will be used.

Mixed-Effect Model Repeat Measurement (MMRM) will be used for the analyses of change and percent change from Baseline in MBL volume to each month. The repeated measures analysis will be conducted using a mixed model including observed measurements at all visits for each month being analyzed. The mixed model includes the categorical fixed effects of treatment, month and treatment-by-month interaction, and the continuous fixed covariate of baseline measurement. The REPEATED statement will be used for month in PROC MIXED with blocks in the covariance matrix identified by subject nested within treatment group. An unstructured variance covariance matrix will be used. Parameter estimation is based on the assumption of data being missing at random and using the method of restrictive maximum likelihood (REML).

Missing data will be imputed using the following methods for the sensitivity analyses of the primary efficacy endpoint:

- Non-Responder Imputation (NRI): All subjects who have missing Final Month MBL volume will be considered as non-responders.
- Observed Cases (OC): The OC analysis will not impute values for missing evaluations, and thus subjects who have missing Final Month MBL volume will be excluded from this analysis.

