Subjects who did not return a sanitary product collection keg (for alkaline hematin menstrual blood loss analysis) at applicable on-site visits (scheduled on-site visit, Product Collection Visit, Unscheduled, or the PD visit) during the study will be asked to indicate whether they had any uterine bleeding or spotting since their last study visit. If the subject did not have uterine bleeding or spotting the site staff will indicate "No" on the UBQ. If the subject did have bleeding or spotting, the subject will be asked the reason why they did not return sanitary product collection keg at the on-site visit. This response will be recorded on the UBQ by the site staff. Subjects who did not return the keg will be retrained on product collection.

Patient Global Impression of Change – Menstrual Bleeding (PGIC-MB)

Subjects will use the PGIC-MB to assess the change in their severity of menstrual bleeding (from very much improved to very much worse) since initiation of study drug.

Columbia-Suicide Severity Rating Scale (C-SSRS)

The C-SSRS² is a systematically administered instrument developed to track suicidal adverse events across a treatment study. The instrument is designed to assess suicidal behavior and ideation and to track and assess all suicidal events, as well as the lethality of attempts. Additional features assessed include frequency, duration, controllability, reason for ideation, and deterrents. Site staff will administer the Screening/Baseline C-SSRS questionnaire in Screening and on Day 1. During the Treatment Period, site staff will administer the C-SSRS Since Last Visit questionnaire at the time points specified in Section 2.2. The C-SSRS administered at the Day 1 Visit will serve as the Baseline for clinical assessment.

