3.22 Return Sanitary Products

Subjects will be required to collect all sanitary products (with or without visible blood) on days with menstrual bleeding or spotting and return them to the clinical study site at visits during the Screening and Treatment periods of the study and at the Premature Discontinuation visit (Section 2). There will be no product collection required during the Follow-up Period.

Subjects will be required to collect and retain all sanitary products on days with menstrual bleeding or spotting (**subjects must be instructed to collect and return all used or worn products even if there is no visible blood on the products or if non-validated products were used**) as described in the Alkaline Hematin Laboratory Manual.

Menstrual Cycle Product Collection Visit

Subjects will visit the site within approximately 5 days after cessation of bleeding or spotting for Menstrual Cycle Product Collection Visit. Sanitary products to measure MBL will be collected, and the site will submit the sanitary products to the alkaline hematin laboratory for analysis of MBL volume. In addition, a venous blood sample will be obtained and sent with the collected products to the alkaline hematin laboratory. It is recommended that site submit the sanitary products to alkaline hematin laboratory only after verifying that subject has qualifying fibroids per central reader based on the local ultrasound report.

In the event that a subject or study personnel cannot come to the site for venous blood sample collection and return of collected sanitary products because of the COVID-19 pandemic, a home health care service may be utilized to obtain such samples.

If the first screening menstrual cycle does not qualify, an additional screening menstrual cycle may be permitted (Table 2). Screening menstrual Cycle 1 for menstrual bleeding assessment begins with the first day of bleeding or spotting associated with menses.

Table 2 Menstrual Blood Loss Volume Eligibility

Screening Cycle 1 Blood Loss	Screening Cycle 2 Blood Loss	Eligible
> 80 mL	N/A	Yes
≤ 80 mL ^a	> 80 mL	Yes

N/A = not applicable

- a. If Screening Cycle 1 blood loss is ≤ 60 mL, study site must consult AbbVie for approval to collect sanitary products for additional menstrual cycles in Screening. Subjects with a Screening Cycle 1 blood loss between > 60 to 80 mL may proceed to collect a second Screening Cycle to determine eligibility without prior approval.

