**Table 1. Monthly Analysis of Bleeding for Amenorrhea**

Time Interval	Amenorrheic Status
Month 1 (Days 2 – 28)	Subject do not bleed or have spotting during Study Days 2 – 28 (Truncated, 27-day window)
Month 2 (Days 29 – 56)	Subject do not bleed or have spotting during Study Days 29 – 56
Month 3 (Days 57 – 84)	Subject do not bleed or have spotting during Study Days 57 – 84
Month 4 (Days 85 – 112)	Subject do not bleed or have spotting during Study Days 85 – 112
Month 5 (Days 113 – 140)	Subject do not bleed or have spotting during Study Days 113 – 140
Month 6 (Days 141 – 168)	Subject do not bleed or have spotting during Study Days 141 – 168
Final Month (last 28 days prior to and including the last dose day)	Subject do not bleed or have spotting during the last 28 days prior to and including the last dose day

Incidence and cumulative incidence of amenorrhea by last bleeding/spotting day at each month will be reported using the categories specified in [Table 2](#).

The summary will be provided including all subjects who have at least 38 days on study drug. If a subject meets the criteria for amenorrhea but discontinues, this subject's amenorrheic status will be carried forward to the time points after the subject has discontinued study drug. The denominator will be the number of subjects who have at least 38 days on study drug and have an amenorrhea status at Final Month.

Plots will be provided by treatment group for percentage of subjects with incidence and cumulative incidence of amenorrhea during the Treatment Period, respectively.

In all the analysis for amenorrhea above, if the observed MBL volume over a window (but treat "Subject only had spotting that did not require the use of sanitary products" on UBQ the same as bleeding) is 0 mL for a subject, then the subject is considered as no bleeding/spotting during that interval. Last bleeding/spotting day refers to the last day with observed AH data > 0 mL or the last day with UBQ indicating bleeding or spotting.

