**Figure D-1. Meta-Analysis for Historical Placebo Data**

For this supportive analysis of the primary endpoint, the principle for borrowing historical sample size is not to exceed the total sample size in the current study while keeping reasonable type I error rate and power with borrowing. Thus, for placebo control borrowing, assuming approximately 90% of subjects with observed primary endpoint data, the historical placebo borrowing sample size will not exceed 42.

Successful hypothesis testing for the primary endpoint will be claimed from Bayesian approach if the posterior probability of rate difference  $> 0$  is larger than 97.5%, i.e.,:

$$P(\theta_{elgolix} - \theta_{placebo} > 0 | data) > 0.975.$$

**Table D-1. Bayesian Type I Error (One-Sided) and Power for Elagolix vs. Placebo (sample size = 28:14, placebo arm rate = 10%, elagolix arm rate = 55%)**

Control Rate	Bias	Error/Power Borrowing 7 subjects	Error/Power Borrowing 14 subjects	Error/Power Borrowing 21 subjects	Error/Power Borrowing 28 subjects	Error/Power Borrowing 42 subjects
0.055	-0.034	0.008/0.985	0.002/0.992	0.002/0.995	0.002/0.998	0.002/0.998
0.064	-0.025	0.012/0.983	0.003/0.992	0.004/0.995	0.004/0.998	0.004/0.998
0.072	-0.017	0.017/0.981	0.005/0.991	0.006/0.995	0.006/0.998	0.006/0.998
0.081	-0.008	0.022/0.979	0.007/0.991	0.009/0.995	0.009/0.998	0.009/0.998
0.089	0.000	0.028/0.977	0.010/0.991	0.013/0.995	0.013/0.998	0.013/0.999
0.098	0.009	0.033/0.976	0.014/0.991	0.018/0.996	0.019/0.998	0.019/0.999
0.106	0.017	0.038/0.974	0.017/0.991	0.023/0.996	0.025/0.998	0.025/0.999
0.115	0.026	0.043/0.973	0.022/0.991	0.030/0.996	0.033/0.999	0.033/0.999
0.123	0.034	0.046/0.971	0.026/0.991	0.036/0.996	0.040/0.999	0.041/0.999
0.132	0.043	0.050/0.970	0.031/0.991	0.044/0.996	0.050/0.999	0.050/0.999
0.140	0.051	0.053/0.969	0.036/0.991	0.051/0.997	0.059/0.999	0.060/0.999

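### Does the SAP turn a woman who did not bleed in the Final Month into missing data for the primary endpoint?

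*SAP*

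**What the plan says.** **Collection.** Operations Manual 3.22 (Protocol Appendix F): "Subjects will be required to collect all sanitary products (with or without visible blood) on days with menstrual bleeding or spotting". A woman without bleeding or spotting therefore has nothing to hand in. Under Operations Manual 3.7, women who return no collection keg "will be asked to indicate whether they had any uterine bleeding or spotting since their last study visit"; site staff record a No on the UBQ if there was none.

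**Primary endpoint.** SAP 8.3.3: "If a subject has missing observed Final Month MBL volume, the Final Month MBL volume will be imputed using multiple imputation". SAP 8.2 adds two sensitivity analyses. In non-responder imputation (NRI), "All subjects who have missing Final Month MBL volume will be considered as non-responders"; the observed-cases analysis drops the same women. Monthly volumes also feed a mixed model for repeated measures (MMRM). None of this text mentions the UBQ or defines when a volume is missing.

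**Bleeding endpoints.** SAP 8.4 does use the UBQ. The amenorrhea rule begins "If a subject does not have evaluable AH data during the last 28 days and no bleeding or spotting" and classes such a woman as amenorrheic. The suppression rule is parallel: "If a subject does not have evaluable AH data during the last 28 days and no bleeding is indicated on UBQ". The text after Table 1 begins "In all the analysis for amenorrhea above, if the observed MBL volume over a window"; it counts a 0 mL window as free of bleeding and spotting, but makes an exception for a UBQ answer of spotting too light to need a product.

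**Planning.** SAP Appendix D sets its sample sizes "assuming approximately 90% of subjects with observed primary endpoint data", giving 28 elagolix and 14 placebo women.

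**The concern.** The endpoint is a volume, and the women who respond most completely produce no volume to measure. Section 8.4 recognises exactly this woman and says how to classify her; Sections 8.2 and 8.3 do not. Read literally, she has no measured Final Month MBL. She would then be multiply imputed in the primary analysis from a model without bleeding status, counted as a failure under NRI, dropped from observed cases, and lose that month in the MMRM. The same woman could be amenorrheic in one table and a non-responder in another.

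Missingness would then be caused by the outcome itself. If freedom from bleeding is commoner on elagolix, the distortion would run against elagolix, and the sensitivity analyses would partly measure a coding choice instead of robustness.

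**Working it through.** **1. The plan's own figure.** Inputs from SAP 2.4: 10% vs 55%, 2:1 allocation, two-sided 5%, 80% power. The weighted mean rate is (0.10 + 2 × 0.55)/3 = 0.40. Placebo size before continuity correction:

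n = [1.96 × √(1.5 × 0.40 × 0.60) + 0.8416 × √(0.10 × 0.90 + 0.55 × 0.45/2)]² / 0.45² = (1.176 + 0.389)² / 0.2025 ≈ 12.1, rounded up to 13.

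The continuity correction raises this to 16 placebo, hence 32 elagolix and 48 in total, as stated. At 32:16 power is 91.1% (pooled z) or 86.5% (Fisher, exact enumeration). Both meet the stated minimum of 80%.

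**2. If no bleeding is scored as 0 mL.** Let B be baseline MBL. Then 0 < 80 mL, and the reduction is (B − 0)/B = 100%, which exceeds 50%. The woman meets both criteria, so the 55% and the power in step 1 stand.

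**3. If she is treated as missing.** Let q be the share of elagolix women affected. The documents do not give q. Assume that all of them are true responders within the 55% and that no placebo woman is affected. The NRI rate is 0.55 − q; the observed-cases rate is (0.55 − q)/(1 − q). As an upper limit take Appendix D's 28 of 32 observed: 1 − 28/32 = 12.5%.

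| q | NRI elagolix rate | Fisher power, NRI | Observed-cases rate |
|---|---|---|---|
| 0 | 55% | 86.5% | 55% |
| 5% | 50% | 77.1% | 52.6% |
| 10% | 45% | 65.6% | 50.0% |
| 12.5% | 42.5% | 59.4% | 48.6% |

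The limit is generous. Ninety percent of 32 is 28.8, which the SAP rounds down to 28, and the shortfall must also cover lost kegs, unreturned products and failed assays.

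**4. Dependence on imbalance.** If the placebo NRI rate also fell, from 10% to 5%, Fisher power would be 92.0%, 85.7% and 81.6% at q = 5%, 10% and 12.5%. At q = 10% that is almost the planned 86.5%.

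**5. The primary analysis.** No valid range follows for multiple imputation. Prior-month MBL is in the model, but on the literal reading a woman's earlier bleeding-free months would be missing too, so her record could hold little to mark her as a non-bleeder. She might be imputed as a responder less often than her observed arm-mates, so the observed-cases rate is not a floor.

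**6. Which reading the text supports.**
- *The 0 mL exception in 8.4.* The UBQ is used only when no keg comes back, yet 8.4 needs an exception for a UBQ spotting answer within an observed 0 mL window. That exception has its main use if windows without a keg already carry an observed 0 mL. Otherwise it reaches only mixed windows, with one keg that reads 0 mL and a separate UBQ.
- *The 90% in Appendix D.* It is applied alike to both arms. At 55% response, 0.55 × 32 = 17.6 elagolix women respond. If women without bleeding counted as missing, at most 4 of those 17.6 could be bleeding-free, with no room for any other cause of missing data. That sits badly with a plan that makes amenorrhea an endpoint, although 90% is a round planning figure and so only weak evidence.
- *The word missing.* The SAP does not define it, so no sentence actually assigns this woman to it.

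**The case for a change.** The best case for a change is that 8.4 describes this woman as having no evaluable alkaline hematin (AH) data, which sounds like missing, and then gives her a bleeding status but no volume. Had every No already become 0 mL, that rule would be unnecessary. The exception after Table 1 is confined to the amenorrhea analyses and argues from 0 mL to no bleeding, not the reverse. One paragraph would settle the matter, no new data are needed, and choosing the rule after unblinding would be post hoc.

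Part of this stands. The derivation is unwritten, as are the value for spotting that needed no product and the link from since-last-visit recall to 28-day windows. The redundancy argument is only partly right: the 8.4 rule also covers assays that could not be evaluated and the answer that products showed no blood, neither of which a plain No would reach. The remaining details are dataset derivations that can be fixed in the programming specification before the single database lock (Protocol 7.1). A short rule in the SAP could also do harm. Crediting a whole keg to one window ignores the daily AH values that 8.4 relies on, and requiring every overlapping UBQ to be negative would make a window missing because of bleeding before it began.

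**Conclusion.** No change to the plan follows. This is a gap in documentation that an analyst fills sensibly: no product and a report of no bleeding is a known 0 mL, not an unknown volume. On that reading the planned response rate, sample size and power are untouched.

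The NRI losses in the table apply only if the literal reading is programmed and every affected woman is on elagolix. They concern a sensitivity analysis with no power claim or decision rule, in a study that Protocol Appendix E calls exploratory. The effect on the primary analysis is unquantified and no error in it has been shown.

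The conclusion rests on 0 mL being the intended derivation. The documents make that the likelier reading but do not prove it, and the programming specifications are not among them. Evidence that women reporting no bleeding are in fact coded as missing would reopen the point.
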